1. PROTOCOL SUMMARY

1.1. Synopsis

A Phase 2, Multicenter, Randomized, Placebo-Controlled, Double-Blind, Proof-of-Concept Study to Evaluate Guselkumab for the Treatment of Subjects with Moderate to Severe Hidradenitis Suppurativa

Protocol number: CNTO1959HDS2001

Guselkumab (CNTO 1959) is a fully human immunoglobulin G1 lambda ($IgG1\lambda$) monoclonal antibody that binds to the p19 protein subunit of human interleukin (IL)-23 with high specificity and affinity. The binding of guselkumab to the IL-23p19 subunit blocks the binding of extracellular IL-23 to the cell surface IL-23 receptor, inhibiting IL-23-specific intracellular signaling and subsequent activation and cytokine production. Guselkumab has been studied in Phase 1, Phase 2, and ongoing Phase 3 studies for the treatment of moderate to severe plaque psoriasis in adults. Guselkumab has been approved for the treatment of adults with moderate to severe plaque psoriasis in the United States, Europe, Canada, and several other countries. Guselkumab is also being studied globally for the treatment of psoriatic arthritis (PsA), Crohn's disease, and pediatric psoriasis.

OBJECTIVES AND ENDPOINTS

Objectives

Primary Objective

The primary objective of this study is to evaluate the initial efficacy, safety, and tolerability of guselkumab in adult participants with moderate to severe hidradenitis suppurativa (HS).

Secondary Objectives

The secondary objectives of this study are:

- To evaluate the efficacy of guselkumab in adult participants with moderate to severe HS during the maintenance phase.
- To evaluate the effect of guselkumab on the dermatologic health-related quality of life in adult participants with moderate to severe HS.
- To evaluate the pharmacokinetics (PK), immunogenicity, and pharmacodynamics (PD) of guselkumab therapy in adult participants with moderate to severe HS.

Endpoints

Primary Endpoint

The proportion of participants achieving Hidradenitis Suppurativa Clinical Response (HiSCR) at Week 16

Major Secondary Endpoints

- The change from baseline in total abscess and inflammatory nodule (AN) count at Week 16.
- The change from baseline in Dermatology Life Quality Index (DLQI) score at Week 16.
- The change from baseline in HS-related pain in the past 24 hours based on Hidradenitis Suppurativa Symptom Diary (HSSD) at Week 16.

Other Secondary Endpoints

- The proportion of participants achieving at least 50%, 75%, 90%, and 100% reduction in total AN count at Week 16.

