Pharmacokinetics a	nd Immunoge	nicity ^{k,l}													
Serum guselkumab concentration		X	X	X	X	X	X	X		X			X		X
Antibodies to guselkumab		X	X	X	X		X			X			X		X
Biomarkers															
Serum biomarkers ^c		X		X			X						X		X

Footnotes:

- a. The screening visit should occur no more than 4 weeks before the Week 0 visit.
- b. The Early Termination Visit should occur approximately 12 weeks after the last administration of study intervention (unless consent is withdrawn).
- c. All study procedures and evaluations are to be completed before study intervention is administered except where otherwise indicated.
- d. Randomization at Week 16 is for placebo group only and will not affect blinding.
- e. IV infusions and SC injections for Weeks 0, 4, 8 and SC injections for Weeks 12 through 36.
- f. The C-SSRS should be completed as the first assessment at screening after signing informed consent and before any tests, procedures, or other consultations, with the exception of the urine pregnancy test, and as the first assessment for baseline and all post-baseline visits, before any tests, procedures, or other consultations, with the exception of the urine pregnancy test, to prevent influencing participant perceptions. DLQI, HADS, HSSD, and PGIC should be performed before any tests, procedures, or other evaluations (Hurley stage, HS-IGA, Lesion counts), with the exception of the urine pregnancy test, for that visit.
- g. Women of childbearing potential must have a negative urine pregnancy test result before randomization and before receiving study intervention at all study intervention administration visits, and at Week 48 or early termination visit.
- h. Photographs to be taken at selected sites for participants who provide an additional consent; if such participants discontinue administration of study intervention early, however, photographs are not required at the final study visit.
- i. A tuberculin skin test is additionally required if the QuantiFERON®-TB test is not approved/registered in the country in which this study is being conducted.
- j. Participants must fast (ie, no food or beverages [except water]) for at least 8 hours before blood is drawn for lipid panel.

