6. STUDY INTERVENTION

6.1. Study Interventions Administered

All participants will receive 1 IV infusion at Weeks 0, 4, and 8 (either active or placebo).

All participants will receive 2 SC injections at each visit (either active, active and placebo, or placebo) every 4 weeks from Weeks 0 to 36.

Intravenous study intervention should be administered over a period of not less than 1 hour, and not more than 2 hours. The infusion should be completed within 6 hours of preparation.

Since 2 SC injections will be administered at each administration visit, each SC injection should be given at a different location of the body.

Detailed instructions on the administration of IV and SC study intervention will be provided in the Site Investigational Product (IP) Binder.

Study intervention administration must be captured in the source documents and the electronic case report form (eCRF).

Guselkumab and placebo will be manufactured and provided under the responsibility of the sponsor. Refer to the IB for a list of excipients.

For details on rescue medications, refer to Section 6.5.1. For a definition of study intervention overdose, refer to Section 8.4, Treatment of Overdose.

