Data that may potentially unblind the intervention assignment (ie, study intervention serum concentrations, anti-guselkumab antibodies, and intervention allocation) will be handled with special care to ensure that the integrity of the blind is maintained and the potential for bias is minimized. This can include making special provisions, such as segregating the data in question from view by the investigators, clinical team, or others as appropriate until the time of DBL and unblinding.

Under normal circumstances, the blind should not be broken until all participants have completed the study and the database is finalized. However, selected sponsor personnel will be unblinded for analysis after the Week 16 DBL has occurred. All site personnel and participants will remain blinded to the treatment assignments until the last participant completes Week 48 evaluations and the database has been locked. The investigator may, in an emergency, determine the identity of the intervention by contacting the IWRS. While the responsibility to break the intervention code in emergency situations resides solely with the investigator, it is recommended that the investigator contact the sponsor or its designee if possible to discuss the particular situation, before breaking the blind. Telephone contact with the sponsor or its designee will be available 24 hours per day, 7 days per week. In the event the blind is broken, the sponsor must be informed as soon as possible. The date and reason for the unblinding must be documented in the appropriate section of the eCRF, and in the source document. The documentation received from the IWRS indicating the code break must be retained with the participant's source documents in a secure manner.

Participants who have had their intervention assignment unblinded by the investigator will not be eligible to receive further study intervention but should continue complete evaluations specified in the Schedule of Activities (Section 1.3).

For the planned interim analyses and the DMC, the randomization codes and the translation of randomization codes into intervention and control groups will be disclosed to those authorized and only for those participants included in the interim analysis.

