6.5.1. Rescue Therapy

In the event that a particularly painful HS lesion occurs that necessitates an acute intervention, investigators will have the option to perform protocol-allowed interventions.

Two types of interventions are allowed:

- Injection with intralesional triamcinolone acetonide suspension (at a concentration of up to 5 mg/mL, up to 1 cc)
- Incision and drainage of the lesion

If incision and drainage is performed, the required over-the-counter soap and water or antiseptic wash should continue to be used. New systemic and topical therapies following incision and drainage (including antibiotics) are prohibited. Concomitant use of wound care dressings is allowed; however, options are limited to alginates, hydrocolloids, and hydrogels. Participants should continue using any ongoing oral and topical therapies (as described in Section 6.5, Concomitant Therapy) during the study.

Concomitant therapies associated with the lesion intervention(s) must be captured in the source documentation and on the appropriate eCRF.

A total of 2 protocol-allowed interventions are permissible through Week 16. An intervention can occur maximally on 2 different lesions at the same visit or on the same lesion at 2 different study visits. The same lesion cannot be treated 2 times at the same visit. If a participant requires more than 2 interventions within the first 16 weeks, then he or she must be discontinued from study interventions but continued for follow-up for approximately 12 weeks after last administration of study intervention.

After Week 16, interventions will not be permitted since all participants will receive active guselkumab treatment. If a participant requires an intervention after Week 16, he or she must be discontinued from study interventions, but continued for follow-up for approximately 12 weeks after last administration of study intervention.

All study visit evaluations must occur before any interventions are performed. Any lesion that undergoes an intervention will be documented in the source.

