Participants who decide to discontinue study intervention administration for reasons other than those outlined above must be interviewed by the investigator to determine if a specific reason for discontinuing study intervention can be identified. Participants should be explicitly asked about the possible contribution of AEs to their decision to discontinue study intervention; investigators should confirm that any AE information elicited has been documented. If a participant elects to discontinue study intervention due to an AE, the event should be recorded as the reason for study intervention discontinuation, even if the investigator's assessment is that the AE would not require study intervention discontinuation. The reason for study intervention discontinuation must be documented in the eCRF and in source documents. Study intervention assigned to a participant who discontinues may not be assigned to another participant.

A participant will not be automatically withdrawn from the study if he or she must discontinue treatment before the end of the treatment regimen. Participants who discontinue study intervention but do not terminate study participation will continue to return for protocol-specified procedures and evaluations for approximately 12 weeks following the last dose of study intervention. The procedures and evaluations listed for the Early Termination Visit should also be performed approximately 12 weeks after the last dose of study intervention.

All procedures and evaluations must be conducted prior to a participant's withdrawal of consent.

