Study intervention administration should be interrupted during the investigation. A positive QuantiFERON®-TB test or tuberculin skin test result should be considered for the detection of latent TB. If the QuantiFERON®-TB test result is indeterminate, the test should be repeated as outlined in the laboratory manual. Participants should be encouraged to return for all subsequent scheduled study visits according to the protocol. Participants who discontinue treatment for latent TB prematurely or who are noncompliant with therapy must immediately discontinue further administration of study intervention and be encouraged to return for all subsequent scheduled study visits according to the Schedule of Activities (Section 1.3).

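### Follow-up that ends about 12 weeks after the last dose leaves participants dosed only at Week 0 without a Week 16 visit, and it conflicts with the follow-up told to two groups of stopped participants

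*Protocol*

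**What the plan says.** The general rule is in Protocol 7.1: participants who stop dosing but remain in the study "will continue to return for protocol-specified procedures and evaluations for approximately 12 weeks following the last dose of study intervention", with the Early Termination procedures done at the end of that time. Schedule of Activities footnotes b and l place the Early Termination or follow-up visit at the same point. Protocol 6.5.1 says of a participant needing more than two rescue interventions in the first 16 weeks that "he or she must be discontinued from study interventions but continued for follow-up for approximately 12 weeks after last administration of study intervention".

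Two other sections say something different about particular stopped participants:

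- Protocol 6.3, repeated in SAP 1.5.2: those unblinded by the investigator "will not be eligible to receive further study intervention but should continue complete evaluations specified in the Schedule of Activities".
- Protocol 8.2.11.2: those who abandon or do not comply with latent TB treatment must stop dosing and "be encouraged to return for all subsequent scheduled study visits according to the Schedule of Activities".

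Both situations are also on the Protocol 7.1 list of reasons for stopping study intervention.

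The primary endpoint is read at Week 16. Under Protocol 9.4.2.1 and SAP 5.3.2, anyone not evaluated at Week 16 is a nonresponder. Under SAP 5.2.3.3.2, missing continuous values are not imputed and are assumed missing at random. The Schedule of Activities has DLQI only at Weeks 0, 16 and 40. Its Early Termination column includes lesion counts but neither DLQI nor HSSD.

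**The concern.** The 12-week limit is counted from the last dose, while the primary endpoint is fixed at Week 16 from randomisation. For the earliest stoppers the first clock runs out before the second. The missing value is then created by the protocol, not by the participant's refusal.

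What is at stake is the Week 16 data of people who would have come. Take two participants who stop for the same reason, such as an unrelated adverse event, one after the Week 0 dose and one after the Week 4 dose. The first is a HiSCR nonresponder because no visit was planned. The second can be scored on lesion counts. The first also has no Week 16 AN count or pain score and no post-baseline DLQI, so three major secondary comparisons rely on a modelling assumption where an observation could have been had. Several mandatory reasons for stopping are reactions to the injection or infusion, so such stops could differ by arm.

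The second issue is consistency. Sites have two follow-up instructions for unblinded participants and for latent TB non-compliers, and nothing says which prevails.

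**Working it through.** **Inputs.**

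- Follow-up after stopping: about 12 weeks from the last dose (Protocol 7.1, 6.5.1, Schedule of Activities footnotes b and l).
- Dosing visits: "every 4 weeks from Weeks 0 to 36" (Protocol 6.1).
- Visit window: ±7 days through Week 36 (Protocol 6.4), so the Week 16 window opens at Week 15. The widest window given anywhere is ±14 days for follow-up visits (SAP 7.1.1.1, Table 3).
- Planning rates 25% and 55%, 60 per arm, two-sided 0.05 (Protocol 9.2, SAP 1.4).

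**Timing.** End of follow-up = week of last dose + 12.

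| Last dose | End of follow-up | Week 16 visit covered? |
|---|---|---|
| Week 0 | 0 + 12 = Week 12 (Week 14 with +14 days) | No: 14 < 15 |
| Week 4 | 4 + 12 = Week 16 (Week 15 if dosed 7 days early) | Yes, at the edge of the window if early |
| Week 8 | 8 + 12 = Week 20 | Yes |
| Week 12 | 12 + 12 = Week 24 | Yes |

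Only the Week 0 row loses the visit, by 16 − 12 = 4 weeks. For the Week 4 row, Early Termination and Week 16 coincide. SAP 2.2 analyses nominal visits and does not say how a visit serving as both is labelled.

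**Who is affected in the primary analysis.** SAP 5.2.3.1 and 5.2.3.2 make a participant a treatment failure after stopping for lack of efficacy or worsening HS, or after starting a prohibited therapy that could improve HS. Such a participant is a nonresponder whether seen or not. That leaves non-failure stops after the Week 0 dose only.

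**What data remain.** Up to Week 12 the schedule has lesion counts and HSSD at Weeks 2, 4, 8 and 12. These enter the repeated-measures models for AN count and pain (SAP 5.4.2.1, 5.4.2.3). DLQI has baseline only, although the DLQI model also uses AN counts (SAP 5.4.2.2).

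**Size on HiSCR.** The documents give no stopping rate. Assume k = 1 to 3 of 60 per arm.

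- Ceiling (all would have responded): k/60 = 1/60 = 1.7 points to 3/60 = 5.0 points.
- At planning rates, p × k/60: placebo 0.25 × 1/60 = 0.4 to 0.25 × 3/60 = 1.25 points; guselkumab 0.55 × 1/60 = 0.9 to 0.55 × 3/60 = 2.75 points. Overall, about 0.4 to 2.8 points.

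**Size on power.** Pooled-variance normal approximation: power = Φ{[Δ√n − 1.96√(2p̄(1−p̄))] / √(p₁(1−p₁) + p₂(1−p₂))}.

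The plan's own case, 25% vs 55%: (0.30 × 7.746 − 1.96 × 0.693)/0.660 = 1.46, giving 92.9% against the stated 93%. The other five rows of Table 1 come out at 84.1, 94.1, 98.4, 81.6 and 98.0% against 85, 94, 98, 82 and 98%.

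Now multiply the response rate by (1 − f), where f is the assumed share scored as nonresponders by absence:

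| f | Both arms | Guselkumab arm only |
|---|---|---|
| 0% | 92.9% | 92.9% |
| 2% (1.2 of 60) | 24.5 vs 53.9: 92.0% | 25 vs 53.9: 91.0% |
| 5% (3 of 60) | 23.75 vs 52.25: 90.6% | 25 vs 52.25: 87.5% |

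**The case against.** The strongest reply is that very few people are involved and the plan already copes. The primary analysis stays fully defined, because absence is nonresponse. SAP 5.3.4 adds an observed-data analysis and a multiple-imputation analysis. At 2% affected, power stays above the stated 90%. The planning-rate figures also assume that one dose works as well as the full course, which is generous for the guselkumab arms. All of this stands, and it limits the size of the point. It does not make the missing visit necessary: the sensitivity analyses drop or impute values that could have been collected.

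It can also be said that Protocol 6.3 refers to the Schedule of Activities, whose footnote b itself sets Early Termination at about 12 weeks, so the two may be read together. That is possible, but the text does not say so, and 8.2.11.2 speaks of all later visits.

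A reader might infer more than the documents support:

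- **That these participants drop out of the AN-count and pain comparisons.** They do not. Their Week 2 to 12 values stay in the models, and only the Week 16 value is missing.
- **That stopped participants in general are told to complete the schedule elsewhere.** Only two named groups are, and the TB group is only encouraged to.
- **That Week 40 suffers an equivalent loss.** Last doses up to Week 24 do end follow-up by Week 36 (24 + 12). But Week 40 carries no test in the SAP's sequence, treatment failures are nonresponders there regardless, and placebo participants who did not receive guselkumab at Week 16 are outside the later summaries (SAP 5.2.5, 5.5.2).

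**Conclusion.** The point holds, within a narrow scope. The 12-week rule removes the Week 16 visit from consenting participants whose only dose was at Week 0, and no visit window in the documents recovers it. In the primary analysis this matters only for stops that are not treatment failures. The clearest loss is DLQI, with no post-baseline value at all.

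On the assumption of 1 to 3 such participants in 60, the effect on an arm's HiSCR rate is at most 1.7 to 5.0 points and more plausibly 0.4 to 2.8. Power falls below the stated 90% only at the upper end of that range and if the loss falls on the guselkumab arm alone. The stopping rate is an assumption throughout.

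The inconsistency between Protocol 7.1 and Protocol 6.3, SAP 1.5.2 and Protocol 8.2.11.2 needs no assumption: the same participants fall under two follow-up rules, and the passages must be reconciled. Both parts are worth correcting because the correction is cheap. Neither threatens the validity of the primary analysis.

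**What to change.** - **Protocol 7.1 and 6.5.1:** state that participants who stop study intervention and have not withdrawn consent attend scheduled assessments through the Week 16 visit or for about 12 weeks after the last dose, whichever is later.
- **Protocol 6.3, SAP 1.5.2 and Protocol 8.2.11.2:** reconcile with that rule, so that unblinded participants and latent TB non-compliers have one stated duration of follow-up.
- **Schedule of Activities and SAP 2.2:** state that when an Early Termination visit falls within the Week 16 window, the Week 16 assessments, including DLQI and HSSD, are done and analysed as Week 16. This serves participants last dosed at Week 4. Those dosed only at Week 0 are served by the first change.

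The cost is protocol and SAP wording, plus one already-scheduled visit off treatment for the few participants stopped after one dose. Nothing in it changes dosing, rescue treatment or the reasons for stopping.

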7.2. Participant Discontinuation/Withdrawal from the Study

A participant will be withdrawn from the study for any of the following reasons:

- Lost to follow-up (Refer to Section 7.3)
- Withdrawal of consent
- Death

To ensure access for participant follow-up, study sites should try to obtain both primary and secondary telephone contact numbers from participants (eg, home, work, and mobile phones), as well as other contact information such as email addresses, and emphasize the importance of follow-up information to the participant, before randomization. For participants who withdraw from study participation, every effort should be made to conduct the Early Termination Visit assessments, as indicated in the Schedule of Activities (Section 1.3). If the reason for withdrawal from the study is withdrawal of consent, then no additional assessments are allowed.

Withdrawal of consent should be a very unusual occurrence in a clinical trial; the investigator should make every effort to maintain good participant relationships to avoid withdrawals of consent. For participants who truly request withdrawal of consent, it is recommended that the participant withdraw consent in writing; if the participant or the participant's representative refuses to do so or is physically unavailable, the study-site should document the reason for the participant's failure to withdraw consent in writing, sign the documentation, and maintain it with the participant's source records. When a participant withdraws before completing the study, the reason for withdrawal is to be documented in the eCRF and in the source document. Study intervention assigned to the withdrawn participant may not be assigned to another participant. Participants who withdraw will not be replaced.

7.2.1. Withdrawal from the Use of Research Samples

The participant may withdraw consent for use of samples for research (refer to Long-Term Retention of Samples for Additional Future Research in Appendix 5 [Section 10.5], Regulatory, Ethical, and Study Oversight Considerations). In such a case, samples will be destroyed after they are no longer needed for the clinical study. Details of the sample retention for research are presented in the main ICF.

